6.4 Safety

The primary objective is to assess the safety of the three different doses of Fesomersen given once a month, which is expected to be maintained during chronic treatment. The primary analysis of the unblinded data snapshot, will be conducted after all participants complete the 24-week main treatment period to assess the safety and PK/PD, and exploratory efficacy of the results. An unblinding plan additional to this SAP will detail the unblinding process and contain the study team members who will be unblinded at the time of the primary analysis.

Additional tables, including participant's extended treatment period up until primary completion, will be presented. No formal interim report will be written.

The final data analysis will be conducted once all participants complete the follow-up period (the last participant's last follow-up visit). At the end of the study completion, statistical analysis will include all data, including the main treatment period, extension period, and the follow-up period as well as distinctive period analysis appropriately.

6.4.1 Analysis of the Primary Safety Variable

The primary analysis is based on a descriptive proportion of subjects with primary endpoints (independently adjudicated) based on SAF analysis set and PA data scope. For each treatment and bleeding category, participants reporting more than one bleeding event will be counted only once using the highest severity. The frequency and percentage of participants with bleeding will be reported where the denominator will be total number of participants in each treatment group.

Estimand for the Primary Safety Endpoint:

The five attributes of the estimand are as follows:

- **Population:** The population consists of ESRD patients as described by the inclusion/exclusion criteria given in study protocol.
- Variable: The incidence of the composite of MB, CRNMB, events during the main treatment period, as assessed by the CIAC
- Treatment: Three dose groups of Fesomersen or placebo on top of standard of care
- Intercurrent events:
 - Unblinding to study intervention: the study allows unblinding of treatment assignment if the investigator deems necessary when related a bleeding or major surgery occur regardless of whether such an event occurs (treatment-policy strategy)
 - Early definitive discontinuation of study intervention or death or kidney transplant: until the occurrence of the intercurrent event (while on treatment strategy)
 - Dose reduction: regardless of whether such an event occurs (treatment-policy strategy).
- **Population-level summary:** Incidence proportion of subjects with an event by study intervention group and differences between Fesomersen treatment groups and placebo group. For the incidence proportions the exact binomial two-sided 95% confidence interval using Blaker's method will be provided. For the difference in incidence proportions the two-sided 95% confidence interval will be presented using the unstratified exact method with the standardized test statistic and inverting a two-sided test (Agresti and Min, 2000).

6.4.1.1 Additional Primary Safety Endpoint(s) Analysis:

Estimand for Time to Event Safety Endpoint:

The attributes constituting the estimand for this endpoint are the following:

- **Population:** The population consists of ESRD patients as described by the inclusion/exclusion criteria given in study protocol.
- Variable:
 - Time from first dose of intervention to MB and CRNMB events (in alignment with ISTH guidelines) up until 28 days after last study intervention
- Treatment: Three dose groups of Fesomersen or placebo on top of standard of care
- Intercurrent events: Of interest is the response to treatment while the participant is
 - o alive (intercurrent event "death") and
 - exposed to study intervention (intercurrent event "premature discontinuation of treatment"),

i.e., both intercurrent events are handled using the same strategy "while alive" or "while on treatment".

Population-level summary:

Death and premature end of exposure to assigned treatment (last administration of assigned treatment plus 28 days) considered a competing event for the safety analysis.

The cumulative incidence function for the event-of-interest as well as the associated competing event(s) together with the corresponding confidence interval will be estimated for each treatment arm using Aalen-Johansen estimators.

The cumulative incidence, i.e. the probability of having a specific event, E, at or before a timepoint, t, $P(T \le t, E = 1)$, will be estimated for time-to-event endpoints by Aalen-Johansen estimators with the competing event.

The difference of the Aalen-Johansen estimators between 40mg Fesomersen and placebo and 80mg Fesomersen and placebo and 120mg Fesomersen and placebo will be presented with a 90% confidence interval.

As the Aalen-Johansen estimator is approximately normal distributed (Aalen, Borgan and Gjessing 2008), the difference of Aalen-Johansen estimators is approximately normal distributed. Thus, the two-sided 90% confidence interval is obtained via:

$$\left[(\widehat{A}J^{TRT}(day) - \widehat{A}J^{Control}(day)) \pm z_{0.95} \sqrt{\sigma^2(\widehat{A}J^{TRT}(day)) + \sigma^2(\widehat{A}J^{Control}(day))} \right]$$

with $\widehat{AJ}^{TRT}(day)$ the Aalen-Johansen estimator for Fesomersen (TRT) at study day, $z_{0.95}$ the 95% quantile of the standard normal distribution and $\sigma^2(\widehat{AJ}^{TRT}(day))$ and $\sigma^2(\widehat{AJ}^{Control}(day))$ are the estimated variances of the Aalen-Johansen estimators at study day, estimated with the Aalen method.

Rates

Cause-specific incidence rates will be calculated for each treatment arm with an 90% confidence interval.

The on-treatment incidence rate will be expressed a "subjects with an event – per 100 participant years". For that the following formula is used:

$$IR_{adj} = \frac{\#Participants with an event}{\sum time under treatment (in days)/(100 * 365.25)}$$

The 90% confidence interval for the exposure-adjusted IR will be computed as

$$\left[\frac{IR_{adj} * \chi^2(0.05; 2e)}{2e}; \frac{IR_{adj} * \chi^2(0.95; 2e)}{2e}\right],$$

with $\chi^2(q; 2e)$ the q quantile of a chi square distribution with 2e degrees of freedoms and e the number of participants with an event. (Nelson 1982)

Hazard ratios

With respect to the cause-specific hazards for the respective safety variable, each of the Fesomersen groups will be compared to the placebo group using two-sided log-rank tests. Due to the explorative nature of these analyses, no multiplicity adjustment will be done.

The cause-specific hazard function $h_k(t)$ is the chance that an individual experiences an event of the primary safety outcome in the next instant in time, given that the individual has not had such an event or a competing event up to time t. Cause-specific hazard ratios, cause-specific relative hazard reduction (csRHR; csRHR = $100 \times [1 - \text{cause-specific hazard ratio}]\%$), and corresponding 2-sided 90% and 95% confidence intervals, comparing the hazards for the event-of-interest in each of the Fesomersen groups with the placebo group will be estimated based on three separate cause-specific Cox proportional hazards models as exploratory amalysis. Censoring will be assumed to be independent form the study intervention. For example, for the comparison of the 120 mg Fesomersen group with the placebo group, the corresponding cause-specific Cox proportional hazards model can be described by the following equation:

$$H_k(t,x_i) = h_{0,k}(t) \exp(\beta_k x_i),$$

where

- $h_k(.)$ cause-specific hazard function for primary safety outcome, as a function of time and subject's covariates
- $h_{0,k}(.) \quad \text{unspecified underlying baseline hazard function for primary safety outcome; hazard of an individual with $x_i = 0$ }$
- t time (in days) relative to the date of first administration
- xi treatment group of subject i
 (0 corresponds to "placebo group" and
 1 corresponds to "120mg Fesomersen group")
- β_k unknown parameter (to be estimated); cause-specific hazard ratio = exp(β_k)

k type of event

Probability

As a supportive analysis, the cumulative incidence functions for the respective event-ofinterest will be compared using the Fine and Grays subdistribution hazards model as well as using the Gray's test.

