4.7 Sample Size Determination

No formal statistical sample size estimates were performed.

The sample size was selected based on prior experience in ESRD with the unconjugated ASO. This study is planned to ensure the safety, tolerability, and PK/PD relationships are assessed adequately while minimizing unnecessary participant exposure. There is no plan for statistical hypothesis testing for this study. In this study, the number of subjects is considered based on the ISIS 416858-CS5 study design.

Approximately 288 participants (96 [72 active+24 placebo] per cohort) will be randomly assigned to study intervention so that an estimated 240 participants will complete the main treatment period. All participants will be randomized to 1 of 3 dose cohorts in a 1:1:1 ratio (Cohort A, Cohort B, and Cohort C). Within each dose cohort, subjects will be randomized in a 3:1 ratio to receive treatment with either Fesomersen or placebo. Considering an approximately 15% dropout rate, an estimated total of 60 participants per intervention group and the placebo group will complete the main treatment period. A participant will be evaluated once he/she was randomized and received at least one dose of study intervention. The number of evaluable and randomized participants is assumed to be similar.

Table 4-1 summarizes 95% expected range for the true population proportion of participants with a composite of MB and CRNMB bleeding. For example, with 60 participants, if 5% of them had a composite of MB and CRNMB bleeding during the main treatment period and the desired confidence level is 95%, the corresponding confidence interval would be \pm 5.51, i.e. the range of 0.0 % to 10.51%. If multiple samples were drawn from the same population and a 95% CI calculated for each sample, we would expect the true population proportion to be found within 95% of these CIs.

Sample Size	Observed Proportion *	Desired Confidence level	Corresponding two-sided confidence interval	Range for the true population proportion
60	2%	95%	±3.54	0.0% to 5.54%
	3%	95%	±4.32	0.0% to 7.32%
	4%	95%	±4.96	0.0% to 8.96%
	5%	95%	±5.51	0.0 % to 10.51%
	6%	95%	± 6.01	0.0% to 12.01%
	7%	95%	± 6.46	0.54% to 13.46%
	8%	95%	± 6.86	1.14% to 14.86%

Table 4-1: Confidence Interval for proportion of participants with a composite of MB and CRNMB Bleeding

CRNMB = clinically relevant non-major bleeding, MB = major bleeding

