* The range of observed proportion is considered based on the Interim report of ISIS 416858-CS5 study where the composite of MB and CRNMB bleeding proportion for Placebo was 5.7% and for total ISIS treated= 4.5% (ISIS treated with 200mg, 250mg and 300 mg doses were 3.8%, 5.6% and 4.0% respectively)

5. Analysis Sets

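### The 90% interval for the Aalen-Johansen bleeding difference (SAP 6.4.1.1) is an untransformed normal interval on about 2 to 4 events per arm, and an arm with no bleed adds zero variance

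*SAP*

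**What the plan says.** SAP 6.4.1.1 estimates the cumulative incidence of major or clinically relevant non-major bleeding in each arm by the Aalen-Johansen method. Death and premature end of exposure are competing events. For each dose against pooled placebo it then argues that "the difference of Aalen-Johansen estimators is approximately normal distributed. Thus, the two-sided 90% confidence interval is obtained via" the estimate plus or minus z(0.95) times the root of the summed variances. The variances "are the estimated variances of the Aalen-Johansen estimators at study day, estimated with the Aalen method". The formula is indexed by day, but no day is named.

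For the primary estimand, SAP 6.4.1 takes a different approach to nearly the same contrast: "For the difference in incidence proportions the two-sided 95% confidence interval will be presented using the unstratified exact method with the standardized test statistic". Each arm's proportion also gets an exact Blaker interval.

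Two other places matter:

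- The opening of SAP section 6 limits cumulative incidences to endpoints with at least one event in a treatment arm. It requires an event in every compared arm only for hazard ratios, the log-rank test and Gray's test. The Aalen-Johansen difference is not named in that second rule.
- SAP 6.4.3 reuses the 6.4.1.1 method for the total-treatment (TA) and overall (OA) data scopes.

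**The concern.** Premature end of exposure is a competing event and not a censoring time. So there should be little censoring before the Visit 22 dose, and each Aalen-Johansen estimate is close to the crude proportion. The interval is then in effect the Wald interval for two small proportions, which is known to be weak at a handful of events. Its variance estimate is zero when an arm has no event.

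In a bleeding-safety trial the upper limit of the excess over placebo is what a reader looks at, and Protocol 4.1 says the primary analysis is meant to speed Phase 3 dose selection. If placebo has no bleed and the drug has several, the printed interval treats the placebo risk as known to be exactly zero.

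**Working it through.** **Inputs**

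- Group size, SAP 4.7: "Approximately 288 participants (96 [72 active+24 placebo] per cohort) will be randomly assigned to study intervention". That is 72 per dose group and 3 x 24 = 72 on pooled placebo.
- Completers, SAP 4.7: "an estimated total of 60 participants per intervention group and the placebo group will complete the main treatment period".
- Planning rates, footnote to SAP Table 4-1: "the composite of MB and CRNMB bleeding proportion for Placebo was 5.7% and for total ISIS treated= 4.5"%; by dose, "ISIS treated with 200mg, 250mg and 300 mg doses were 3.8%, 5.6% and 4.0% respectively".

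**The plan's own figure.** The documents give no number for the Aalen-Johansen difference. The nearest is Table 4-1 for one proportion at 5% and n = 60: 1.96 x sqrt(0.05 x 0.95/60) = 5.51 points. This matches, as do the other six rows.

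**Expected events.** Placebo: 72 x 0.057 = 4.1. Active: 72 x 0.038 = 2.7 to 72 x 0.056 = 4.0. With 60 per arm: 3.4, and 2.3 to 3.4.

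**Is the interval really Wald?** For an arm of 72 with 4 bleeds and 11 competing events, the Aalen-Johansen estimate is 5.56%, equal to 4/72. Its standard error is 2.72 points, against a binomial sqrt(0.0556 x 0.9444/72) = 2.70. So the binomial form is used below.

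**Worked intervals, n = 72 per arm, drug minus placebo, 90%, in points**

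- 4 v 4, SAP formula: 0 ± 1.645 x sqrt(2) x 2.70 = ±6.28. Score ±7.03; exact by the 6.4.1 method about ±7.2.
- 6 v 2: upper limit 11.8 by the SAP formula, 13.1 by complementary log-log MOVER, 13.0 exact.
- 4 v 0: the placebo variance is 0, so 5.56 ± 1.645 x 2.70 = 1.12 to 10.00. Upper limit by score 11.8, MOVER 12.2, exact about 12.4.
- 0 v 0: 0 to 0 by the SAP formula. Score ±3.65; MOVER ±4.1.
- 0 v 4: upper limit -1.12 by the SAP formula, about -1.6 exact, -0.45 by MOVER.

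For scale, the one-sided 95% upper bound for 0/72 is 1 - 0.05^(1/72) = 4.1%.

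**Coverage and upper miss.** Full enumeration of two binomials, n = 72. Upper miss is the probability that the upper limit lies below the true difference (nominal 5%).

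| Drug v placebo | SAP coverage | SAP upper miss | MOVER coverage | MOVER upper miss |
|---|---|---|---|---|
| 3.8% v 5.7% | 87.8% | 5.1% | 94.2% | 2.9% |
| 4.0% v 5.7% | 90.4% | 4.6% | 94.4% | 2.6% |
| 4.5% v 5.7% | 90.0% | 4.1% | 93.3% | 3.5% |
| 5.6% v 5.7% | 88.4% | 6.1% | 93.8% | 2.9% |
| 10% v 5.7% | 88.7% | 6.1% | 92.1% | 4.0% |
| 15% v 5.7% | 89.0% | 6.5% | 91.8% | 4.4% |
| 8% v 2% | 87.6% | 8.5% | 95.2% | 2.9% |

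The first four rows use the documents' rates; the last three are assumptions. With 60 per arm, SAP coverage at the documents' rates is 87.2% to 90.3% and upper miss 4.0% to 6.2%.

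**How often is an arm empty?** P(no bleed in 72) = 0.943^72 = 1.5% on placebo; for active arms it runs from 0.944^72 = 1.6% to 0.962^72 = 6.2%. P(either arm empty) = 1 - (1 - 0.0146)(1 - 0.0158) = 3.0% up to 1 - (1 - 0.0146)(1 - 0.0615) = 7.5%.

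**The case against.** **The result that matters is already protected.** This stands. The interval is an additional, descriptive analysis in a study with no hypothesis test and no margin. The primary difference has an exact 95% interval: its upper limit at 4 v 4 is about 9.0 points, well beyond the 6.28 here.

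**The upper limit is not always too low.** This also stands. A reader might infer a systematic bias in the drug's favour, but the documents' rates do not show one: upper miss is 4.1% to 6.1%, and 4.1% at 4.5% v 5.7% is slightly conservative. With 0 bleeds on drug and 4 on placebo, the SAP's upper limit (-1.12) is above the exact one (about -1.6). The 8.5% miss needs a 2% placebo rate, about a third of the documented 5.7%.

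**Section 6 may already exclude the empty arm.** Only partly. Read per arm, its event rule means no cumulative incidence is calculated for an arm without a bleed, so the zero-variance interval never appears. But then no difference is reported when placebo has no bleed and the drug has several. Read as any arm, the interval is produced. The stricter wording for hazard ratios and tests favours this second reading. The text does not settle it.

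**The replacement is further from nominal.** True at the documents' rates: MOVER covers about 93% to 94%, an error of about 3 to 4.4 points, against at most 2.2 for the SAP formula. The case for it is that it removes the false zero variance, keeps upper miss at or below 4.4% in every case tried, and errs in the same direction as the exact method chosen in 6.4.1.

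**Little censoring is an assumption.** Protocol 7.2 says outcomes are censored at early termination, so the match to a crude proportion is approximate.

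**Conclusion.** The concern holds in a limited form. The formula is a plain normal interval on about 2 to 4 expected events per arm. At the documented rates its coverage is about 88% to 90% and its upper miss about 4% to 6%. The upper miss is about 6% to 6.5% if drug bleeding is 10% to 15% against 5.7% on placebo, and larger if placebo bleeding is rarer. The clear error is the arm with no bleed. It occurs in about 3% to 7.5% of comparisons at the documented rates, understates the 4 v 0 upper limit by about 2.2 to 2.4 points, and gives an interval of zero width at 0 v 0.

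The documents do not support reading this as a flaw in the primary bleeding result, or as an upper limit that is always too favourable.

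The figures assume 72 per arm, rates like those of the predecessor study, a binomial approximation to the Aalen-Johansen estimate, and no administrative censoring before the evaluation day. The missing evaluation day is a gap whichever interval is used: under SAP 4.5.1 participants who enter the extension leave the main period at their Visit 22 dose, so few remain at risk in the main-period (PA) scope afterwards.

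**What to change.** In SAP 6.4.1.1, replace the interval formula.

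1. For each arm, compute 90% limits (l, u) for the cumulative incidence F on the complementary log-log scale, using the Aalen variance. If the arm has no event, set l = 0 and u to the exact binomial one-sided 95% upper limit.
2. With d = F1 - F2, combine by MOVER: lower = d - sqrt((F1 - l1)^2 + (u2 - F2)^2); upper = d + sqrt((u1 - F1)^2 + (F2 - l2)^2).
3. State that the difference is reported when one arm has no event, and amend the event rule at the start of section 6 to agree.
4. Name the evaluation day for each data scope. Day 168 suits PA, because it precedes the Visit 22 dose on Day 169. One day cannot serve all three scopes, so TA and OA each need their own stated day.

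The cost is a few lines of text and code. The intervals become wider and mildly conservative, with about 92% to 95% coverage in most cases tried and more at very low rates.

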In addition, exposure adjusted bleeding rate analysis will be performed for the primary endpoint (for example, 100 person-years bleeding rate) and for the MB, CRNMB, minor bleeding, separately.

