4.5 Data Rules

4.5.1 Analysis Dates

For the study, the following date and time window are of relevance for the analysis:

• End of Study Date

The end of the study is defined as the date the last participant completes the last protocol-defined visit/contact.

• Primary Completion Date

The primary completion date is the date when the last participant completes the main treatment period . See the below period definitions for data collection in each period.

• Main Treatment Period (actual)

The main treatment period includes a total of 24 weeks

For subjects who *did not* enter the extension period the main treatment period is defined as the period from first dose of study intervention to the last date of dose +28 days.

For subjects who *did* enter the extension period the main treatment period is defined as the period from first dose of study intervention to the administration of study intervention (and hence commencement of the extension period), at visit 22.

• Extended Treatment Period (actual)

The extended treatment period includes a total of up to 24 weeks, from study intervention administration on visit 22 until the date of last dose +28 days or date of last contact (whichever comes first).

• Post-Treatment Follow-up Period (actual)

The post-treatment follow-up period includes a total of 16 weeks. For subjects who *did not* enter the extension period, the follow up is defined as the period from the end of the main treatment period +1 day to the last contact date.

For subjects who *did* enter the extension period, the follow up is defined as the period from the end of extension period + 1 day to the last contact date.

For each subject, the following individual dates are of relevance for analysis:

• Randomization date:

The date of randomization as recorded in the IxRS system.

• Date of the first dose of study intervention:

The date of the first dose of Fesomersen or placebo will be used from the appropriate eCRF page capturing the study intervention.

Date of the earliest logically possible dose of study intervention administration will be used, in cases where the date of the first dose is missing or incomplete.

• Date of the last dose of study intervention:

The date of the last dose of Fesomersen or placebo will be used from the appropriate eCRF page capturing the study intervention.

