6.4.3 Sensitivity and Supplementary Safety Analysis

To support the primary study results and to assess the robustness of the analysis, several additional sensitivity and supplementary analyses will be performed.

The primary safety endpoint will be analyzed using the same method described in Section 6.4.1.1 based on SAF analysis set and both TA and OA data scope.

In addition, analysis will be performed with additional bleeding events on SAF analysis set with PA data scope, and SAF analysis set with TA data scope:

- Minor bleeding
 - Minor bleeding will be further categorized as injection site and non-injection site bleeding events.

Additional analysis on the secondary safety endpoints will be performed based on SAF analysis set and TA data scope.

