6.5 Data affected by the war in Ukraine

Data 'affected' by the war in the Ukraine will be assessed during the final Blind Review Meeting and will be documented in the Blind Review Report. As the war started after the primary analysis was completed, it is expected that only data in the post study intervention follow-up period will be affected, the impact of the war is considered to be minor/not substantial on the statistical analysis and on interpretation on the study results. Any missingness due to the war is considered as not related to the outcomes of the study i.e. the missingness is likely noninformative. The EMA guidance "Points to consider on the impact of the war in Ukraine on methodological aspects of ongoing clinical trials" released by the Biostatistics Working Party will be taken into account.

7. Document History and Changes in the Planned Statistical Analysis

Protocol No.: BAY 2976217/21170

- Approval of the SAP version 1.0 dated 25 AUG 2020
- The following changes were made in the SAP Version 2.0 dated 15 DEC 2021:
 - Updated the data scope definitions to cover the follow up and extension periods alone.
 - Updated the concomitant medication period definitions
 - Adapted the safety and efficacy outcome variable sections with the exploratory competing risk analysis including with cause-specific and sub-distribution hazard models
 - \circ Clarified definition of the subgroup of subjects with COVID-19
 - General updates based on new version of the protocol
 - \circ $\;$ Updates to the PK/PD sections based on expert opinion and review
 - o Updated BAY 2976217 to 'Fesomersen'.
 - \circ $\,$ Removed the following subgroups as they do not make sense
 - Medical condition that likely led to RRT
 - Time since the start date for most recent Hemodialysis (including hemodiafiltration)
 - Removed text from section 6.4.3 due to repetition and referenced the text in section 6.4.1.
 - Updated the safety analysis set definition to clarify how subjects who were mis-dosed would be handled
- The following changes were made in the SAP version 3.0 dated 01 FEB 2022:
 - Added undetermined- presumed cardiovascular death to efficacy composite
 - Updated analysis periods and data scopes so they no longer depend on visits
 - Aligned the subgroups across safety and efficacy analyses
- The following changes were made in the SAP version 4.0 dated 31MAY2022:
 - Added section 6.5 relating to the handling of data affected by the war in Ukraine.

8. References

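### The 90% interval for the exposure-adjusted bleeding rate uses 2e degrees of freedom for its upper limit; follow-up ends by time, so the exact Poisson upper limit needs 2e+2

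*SAP*

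**What the plan says.** Under Rates in SAP 6.4.1.1, the on-treatment rate is the number of participants with an event divided by total time under treatment, per 100 participant-years. The interval is introduced with "The 90% confidence interval for the exposure-adjusted IR will be computed as", and the formula is

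[ IR_adj × χ²(0.05; 2e) / (2e) ; IR_adj × χ²(0.95; 2e) / (2e) ],

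where χ²(q; 2e) is "the q quantile of a chi square distribution with 2e degrees of freedoms and e the number of participants with an event". Both limits therefore use 2e degrees of freedom.

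Observation is closed by the calendar. For participants who do not enter the extension, SAP 4.5.1 defines the main treatment period as "the period from first dose of study intervention to the last date of dose +28 days"; for those who do, it ends at the Visit 22 dose. SAP 4.5.2 leaves later events out of the primary data scope. Neither document stops follow-up at a set number of events, and neither gives a different upper limit elsewhere.

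SAP 6.4.3 analyses the primary safety endpoint again "using the same method described in Section 6.4.1.1 based on SAF analysis set and both TA and OA data scope". Protocol 9.4.2 also plans exposure-adjusted rates for major bleeding, clinically relevant non-major bleeding and minor bleeding separately, without specifying an interval.

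**The concern.** The formula belongs to a different sampling scheme. With observation stopped at the e-th event, e is fixed, total exposure is random, and 2e degrees of freedom is right at both ends. With observation stopped by time, e is random. The upper limit is then the mean at which e or fewer events would have probability 5%, which is χ²(0.95; 2e+2)/2 on the count scale. Because 2(e−1)+2 = 2e, the SAP gives e events the upper limit that belongs to e−1.

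For a bleeding rate, the upper limit tells the reader how much harm the data still allow. It is the limit that is too low, and the error is largest at the small counts this trial expects. Protocol 4.1 says the primary analysis serves Phase 3 dose selection, so bleeding rates that look better bounded than they are would be unhelpful there.

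**Working it through.** **Inputs.** Two-sided 90%, 5% per tail (SAP 6.4.1.1). 72 participants per active dose and 3 × 24 = 72 pooled placebo; about 60 per group after roughly 15% dropout (SAP 4.7). Main treatment period 24 weeks = 168 days (SAP 4.5.1). Planning proportions for the composite: 5.7% on placebo and 3.8% to 5.6% by active dose (footnote to SAP Table 4-1). The SAP gives a formula but no worked interval, so the figure to test is the nominal 90%.

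**Where 90% is reproduced.** Simulating follow-up that stops at the e-th event, the SAP formula covers 89.9% to 90.1% of the time for e = 3, 4 and 6. It does what it promises under that scheme.

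**Expected counts here.** 72 × 0.038 = 2.7 and 72 × 0.057 = 4.1 participants with an event per group.

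**Limits on the count scale.** SAP upper limit χ²(0.95; 2e)/2; exact upper limit χ²(0.95; 2e+2)/2; the mid-P limit solves P(X < e) + ½P(X = e) = 0.05. The lower limit χ²(0.05; 2e)/2 is common to the SAP and exact intervals and has exactly 5% in its tail.

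| e | Lower | SAP upper | 2e+2 upper | Mid-P upper | Shortfall vs 2e+2 | Shortfall vs mid-P | P(X ≤ e) at SAP upper |
|---|---|---|---|---|---|---|---|
| 1 | 0.051 | 2.996 | 4.744 | 4.113 | 37% | 27% | 20.0% |
| 2 | 0.355 | 4.744 | 6.296 | 5.689 | 25% | 17% | 14.8% |
| 3 | 0.818 | 6.296 | 7.754 | 7.161 | 19% | 12% | 12.7% |
| 4 | 1.366 | 7.754 | 9.154 | 8.570 | 15% | 10% | 11.5% |

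The last column should be 5%. Exposure cancels from the percentage shortfalls, so dropout does not change them. Each SAP upper limit equals the 2e+2 limit one row above.

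**On the rate scale.** Assume full exposure: 72 × 168 / 365.25 = 33.1 person-years.
- e = 3: rate 3/33.1 = 9.06 per 100 person-years; SAP interval 2.47 to 19.0; with 2e+2, 2.47 to 23.4.
- e = 4: rate 12.08; SAP interval 4.13 to 23.4; with 2e+2, 4.13 to 27.6.

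**Coverage.** Poisson counts, given at least one event, because SAP section 6 restricts rates to endpoints with an event. At n = 72 and true risks of 3.8, 4.0, 4.5, 5.0, 5.6 and 5.7%, the SAP interval covers 97.7, 97.1, 81.9, 86.7, 90.4 and 90.6%. Averages over an evenly spaced grid:

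| True risk | n | SAP coverage (minimum) | SAP: true rate above upper limit | 2e+2 coverage |
|---|---|---|---|---|
| 3.8–5.7% | 72 | 87.9% (80.7%) | 8.7% | 96.6% |
| 3.8–5.7% | 60 | 91.5% (80.7%) | 5.0% | 96.5% |
| 2–8% | 72 | 90.6% (80.7%) | 6.0% | 95.9% |
| 2–8% | 60 | 92.0% (80.7%) | 4.5% | 96.4% |

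**Closer to the design.** Simulating 72 participants with first events only, exponential event times and 15% exponential dropout (assumed shapes), coverage given at least one event was 86.2% at a true proportion of 4.5% and 87.9% at 5.7%. With 2e+2 it was 96.9% and 96.4%.

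**The case against.** The SAP promises a 90% interval and does not call this one exact. The 2e+2 limit is itself exact only for a Poisson count over fixed exposure; here only first events count and exposure is random, so it is slightly approximate and conservative. Averaged over 2–8%, the range of SAP Table 4-1, the SAP interval comes close to 90%, while 2e+2 behaves like a 96% interval. No hypothesis is tested, no threshold is attached to the rate, and the same question is answered by the proportion with its Blaker interval, the exact difference intervals and the Aalen-Johansen curves. The gap narrows as events accumulate (11% at e = 6, 7% at e = 10), which softens the effect in the longer data scopes. Carrying the formula to major bleeding alone is an inference, since the protocol specifies no interval there.

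Much of this stands, and it limits the importance of the point. It does not rescue the formula. The averages near 90% leave out samples with no event, mix over- and under-coverage, and still hide dips to about 81%. The upper limit lies below both the 2e+2 limit and the less conservative mid-P limit at every count examined, so the shortfall does not depend on preferring a conservative method.

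**Conclusion.** The concern holds. The upper limit in SAP 6.4.1.1 is built for follow-up ended by event count, and this trial ends follow-up by time. At 3 to 4 participants with an event per group, the limit is 15% to 19% below the exact Poisson limit and 10% to 12% below mid-P; at 1 or 2 events it is 25% to 37% below the exact limit. The percentages follow from the formula alone. The per-100-person-year examples assume full exposure, and the expected counts assume the planning rates from the earlier trial. Realised coverage depends on the true rate and group size and is sometimes above 90%.

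If the same formula is used for major bleeding alone, the shortfall is at least as large, because that count cannot exceed the composite. This is worth correcting, but it affects a supportive analysis: no primary result changes.

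**What to change.** In SAP 6.4.1.1, set the upper limit to IR_adj × χ²(0.95; 2e+2)/(2e) and keep χ²(0.05; 2e) for the lower limit. Use the same rule wherever the 6.4.1.1 rate is repeated, and say whether it applies to the separate bleeding categories. Optionally, for an arm with no event, where the present expression is 0/0, report a lower limit of 0 and an upper limit of χ²(0.95; 2)/2 = 3.00 divided by exposure.

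The statistical cost is wider intervals: upper limits rise by 58%, 33%, 23% and 18% at e = 1 to 4, and average coverage over 3.8–5.7% becomes about 96.6% at n = 72. If that is too conservative, specify mid-P limits instead.

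The practical cost is one line of code, a documented SAP change and rerun rate tables. SAP 6.5 includes the words "As the war started after the primary analysis was completed", so the change comes after the unblinded snapshot and should be labelled that way. It applies identically to every arm, including placebo.
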